The percent of symptom-free 24-hour periods for this example is derived as $2.5/5 * 100\% = 50\%$. Similar rules apply to on-therapy interval.

Percentage of Asthma-control Days (24-Hour Periods):

Asthma-control days are defined as scores of zero recorded on the asthma symptom score diary during the 24-hour period and no rescue medication usage during the same 24-hour period. The baseline is defined as the percentage of asthma-control days over the 7 days prior to randomization. Detailed imputation rules are specified in [Table 3](#).

Table 3: An Example of Baseline Electronic Patient Diary for Asthma-control days

Analysis Day	Total Daily Asthma Score / Rescue Medication Usage	Value used for numerator of percentage calculation	Value used for denominator of percentage calculation
-1	3 / 0	0	1
-2	Missing / 0	Not used in calculations	Not used in calculations
-3	0 / 0	1	1
-4	Missing / 3	0	1
-5	0 / 3	0	1
-6	3 / 3	0	1
-7	Missing / Missing	Not used in calculations	Not used in calculations
Week's total		1	5

The percent of asthma-control days for this example is derived as $1/5 * 100\% = 20\%$. Note that if a patient's asthma score is missing, and there is no rescue medication usage during the same 24-hour period, the asthma-control days will not be used in calculations.

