6.3.1.3. Asthma Symptom Score

Asthma symptom scores will be recorded in the patient's electronic patient diary each morning and each evening before determining PEF and before administration of IMP or rescue medications.

Daytime Symptom Score (determined in the evening):

- 0=No symptoms during the day
- 1=Symptoms for 1 short period during the day
- 2=Symptoms for 2 or more short periods during the day
- 3=Symptoms for most of the day which did not affect my normal daily activities
- 4=Symptoms for most of the day which did affect my normal daily activities
- 5=Symptoms so severe that I could not go to work or perform normal daily activities

Nighttime Symptom Score (determined in the morning):

- 0=No Symptoms during the night
- 1=Symptoms causing me to wake once (or wake early)
- 2=Symptoms causing me to wake twice or more (including waking early)
- 3=Symptoms causing me to be awake for most of the night
- 4=Symptoms so severe that I did not sleep at all

To calculate total daily asthma symptom score, analysis days are defined in [Table 4](#). The total daily asthma symptom score is the average of the daytime and the nighttime scores. The total daily asthma symptom score will be considered missing if either the daytime or nighttime score is missing.

The weekly average will be calculated as the sum of total daily asthma symptom scores over the 7 days for each analysis week divided by the number of nonmissing assessments.

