6.4.1.3. Percentage of Asthma-control 24-Hour Periods

An asthma-control 24-hour period is defined as a 24-hour period with asthma symptom scores of zero and no rescue medication use as recorded in the electronic patient diaries. The calculations of the percentage of asthma-control 24-hour periods will be based on the weekly analysis day data recorded during the treatment period. The missing data will be imputed according to the rules specified in Table 3. A minimum of 60% of full days during the 12-week treatment period (or relative to the number of days that the patient participated in the study) cannot be missing in order for a patient to be included in this analysis.

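### SAP Table 3 keeps a day with a missing symptom score only when rescue was used, so missing-score days can only lower the percentage of asthma-control days relative to leaving them out

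*SAP*

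**What the plan says.** SAP 4.2 defines an asthma-control day by "scores of zero recorded on the asthma symptom score diary during the 24-hour period and no rescue medication usage during the same 24-hour period". Table 3 then sets out how incomplete days are handled in a seven-day example:

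- Score missing, rescue 3 (day -4): kept, numerator 0, denominator 1.
- Score missing, rescue 0 (day -2): left out. The note repeats that if the "asthma score is missing, and there is no rescue medication usage during the same 24-hour period, the asthma-control days will not be used in calculations".
- "Missing / Missing" (day -7): left out.

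The example result is 1/5 = 20%. Table 3 has no row for a recorded score with a missing rescue entry.

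On the score itself, SAP 6.3.1.3 says: "The total daily asthma symptom score will be considered missing if either the daytime or nighttime score is missing". For the treatment period, SAP 6.4.1.3 says: "The missing data will be imputed according to the rules specified in Table 3". It also sets a floor for inclusion: "A minimum of 60% of full days during the 12-week treatment period" must be non-missing, or that share of the days on which the patient took part. SAP 6.4.2.4 compares the change from baseline between arms with a Wilcoxon-Mann-Whitney test.

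**The concern.** Rescue use makes a day a failure whatever its symptom score, so keeping day -4 looks natural. The difficulty is what happens to the other missing-score days. With rescue 0 they could be successes or failures, and all of them are removed. Among days with no score, only failures remain, so the percentage is pulled down even when scores are missing completely at random.

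Nor does the rule keep known failures consistently. Take a day with one half-day score of 2, the other half-day score missing and rescue 0. It cannot be an asthma-control day. Its total score is nevertheless missing under 6.3.1.3, so Table 3 drops it.

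At stake is the level of the endpoint in each arm and, if partly recorded days are more frequent in one arm or period than another, the comparison of change from baseline.

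**Working it through.** **1. The SAP's example (Table 3).**

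| Day | Score / rescue | SAP rule | Fully recorded days only |
|---|---|---|---|
| -1 | 3 / 0 | 0/1 | 0/1 |
| -2 | Missing / 0 | out | out |
| -3 | 0 / 0 | 1/1 | 1/1 |
| -4 | Missing / 3 | 0/1 | out |
| -5 | 0 / 3 | 0/1 | 0/1 |
| -6 | 3 / 3 | 0/1 | 0/1 |
| -7 | Missing / Missing | out | out |
| Total | | 1/5 = 20% | 1/4 = 25% |

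The SAP figure reproduces. The one retained missing-score day costs 5 points.

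**2. Direction.** A missing-score day either contributes nothing or changes x/n to x/(n+1). The second is never larger, and is equal only when x = 0.

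**3. Size.** The documents give no rates for control, rescue use or diary gaps, so every input here is assumed:

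- p: true share of asthma-control days
- r: probability of rescue use on a day
- m: share of days with a missing total score, missing at random
- q: share of those days on which rescue is still recorded

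Successes counted: (1-m)p. Days counted: (1-m) + mqr. The rule therefore returns

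(1-m)p / [(1-m) + mqr].

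Placebo, p = 35%, r = 55%, m = 20%:

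- q = 1: 0.28 / (0.80 + 0.11) = 30.8%
- q = 25%: 0.28 / (0.80 + 0.0275) = 33.8%

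A simulation with p = 40%, r = 40%, m = 20%, q = 1 gave 36.4% under the rule and 40.1% on complete days, against a true 40.1%. The formula gives 0.32/0.88 = 36.4%.

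**4. Difference between arms.** Active arm assumed p = 50%, r = 40%, so the true difference is 50 - 35 = 15.0 points.

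| Gaps (active, placebo) | q | Active | Placebo | Difference |
|---|---|---|---|---|
| 20%, 20% | 1 | 0.40/0.88 = 45.45% | 0.28/0.91 = 30.77% | 14.7 |
| 20%, 20% | 25% | 0.40/0.82 = 48.78% | 0.28/0.8275 = 33.84% | 14.9 |
| 15%, 30% | 1 | 0.425/0.91 = 46.70% | 0.245/0.865 = 28.32% | 18.4 |
| 15%, 30% | 25% | 0.425/0.865 = 49.13% | 0.245/0.74125 = 33.05% | 16.1 |
| 30%, 15% | 1 | 0.35/0.82 = 42.68% | 0.2975/0.9325 = 31.90% | 10.8 |

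The last row reverses the gaps: the difference can shrink as well as grow.

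**5. Change from baseline.** The same rule applies in both periods, so part of the bias cancels. Suppose placebo control stays at 35% while gaps rise from 20% to 30%. The spurious change is 28.32 - 30.77 = -2.45 points at q = 1, although the on-treatment level is too low by 35 - 28.32 = 6.68 points. At q = 25% the spurious change is 33.05 - 33.84, about -0.8 points.

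**The case against.** The strongest defence is that rescue use settles a day's status, so keeping day -4 uses observed data, in line with SAP 4.3.1. If children skip entries on bad days, a complete-day rule would overstate control, and Table 3 would partly offset that. It is true that no complete-day rule is unbiased under every mechanism. But this does not justify a rule that keeps some certain failures and drops others, and any offset would be accidental.

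The defence is stronger on size. Symptom scores and rescue use are entered in the same morning and evening handheld sessions (SAP 2.1). A child who misses both sessions has neither item, and Table 3 drops that day without bias. Bias needs a missing score together with a recorded rescue count above 0. The SAP does not say how a 24-hour rescue total is formed when one session is missed, so q cannot be inferred; q = 1 is a ceiling.

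A reader might infer more than the documents support:

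- That every partly recorded day lowers the percentage. This is shown only for missing-score days, because Table 3 has no row for missing rescue with a recorded score.
- That 20% is a lower bound on the truth. If day -2 was really a failure, the figure with it included is 1/6 = 16.7%.
- That falling diary compliance in general will look like worsening control. Wholly missed days have no such effect.
- That an arm could plausibly average 40% missing. The 60% floor applies to each patient, so every included patient would have to sit at the limit. The contrast with baseline is also modest: the randomization criterion of 5 of 7 days (Protocol 5.9) already allows 2/7 = 29% missing, and SAP 4.2 notes that a few patients were randomized with fewer than 5 values.
- That the rule favours active treatment. This would need unequal gaps, for which there is no evidence either way.

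**Conclusion.** The point holds as a minor flaw in one derivation. Table 3 makes retention of a missing-score day depend on its outcome and applies that idea unevenly. The direction of the bias in the level, relative to leaving such days out, follows from the rule itself.

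The size rests on assumed p, r, m and q and on scores missing at random. At 20% missing, the assumed placebo level of 35% falls by 4.2 points at q = 1 and by about 1.2 points at q = 25%. The arm difference is nearly unchanged with equal gaps. With gaps of 15% active and 30% placebo it becomes 18.4 points at q = 1 or about 16.1 at q = 25%, against a true 15.0.

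The endpoint is one of the other efficacy endpoints, with no multiplicity adjustment (SAP 7.2). No primary or secondary conclusion depends on it.

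**What to change.** Change Table 3 and its note so that a day enters the numerator and denominator only when both the total symptom score and the full 24-hour rescue entry are recorded. Day -4 then becomes a day not used, and the example becomes 1/4 = 25%. State in 6.4.1.3 that the same rule holds on treatment. This removes the bias under random missingness and also settles the case of a recorded score with missing rescue.

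The cost is an edit to one table, its note and one derivation. The small downside is that a few partly recorded days, including some whose status is known, no longer contribute.

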4.3. Handling Withdrawals and Missing Data

4.3.1. Missing Data Imputation for Efficacy Analysis

The primary analysis and sensitivity analyses for the primary endpoints include reference-base multiple imputations for missing data and tipping point approaches as detailed in Section 6 and [Appendix A](#).

For endpoints analyzed using the mixed model for repeated measures (MMRM), there will be no imputation for missing data.

For all other variables, only the observed data from the patients will be used in the statistical analyses (ie, there is no plan to estimate missing data).

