4.3.2. Study Days and Visit Windows

Study days are numbered relative to the first day of IMP administration. The start of treatment (Day 1) is defined as the date on which a patient takes the first dose of IMP. Days will be numbered relative to treatment start (ie, ..., -2, -1, 1, 2, ...; with day 1 being the first day of IMP administration and day -1 being the day before the first day of IMP drug administration).

For data collected at the investigational center visits, such as RV (TV1), TV2 to TV6/IMP DV, efficacy and safety data will be analyzed using the visit recorded in the case report forms (CRFs) unless otherwise stated for by-visit summaries. If there are multiple assessments at a postbaseline visit, then the last nonmissing assessment at that visit will be used for the summary. This includes assessments at scheduled and unscheduled visits (the reason for the unscheduled visit has to be included for that particular assessment). If there are both scheduled and unscheduled visits with nonmissing results at the specific visit, the last nonmissing assessment will be used for the summary. For the purpose of the efficacy analysis, assessments collected at the

unscheduled early termination visit will be assigned to the next scheduled visit and also used as the final assessment for the final assessment summaries.

For the analysis of electronic patient diary recorded data (ie, pulmonary function test [PFT], rescue medication usage and asthma symptom score, etc.), the day used for analysis consists of the evening assessment for the date of the first dose of IMP and the morning assessment for the following day as illustrated in [Table 4](#).

Weekly average data will be generated using 7-day windows based on study days (before and after the first dose of double-blind IMP). For example, week 6 will start from day 36 to day 42. A summary will be provided using the derived week window.

Table 4: Analysis Day

Analysis day	Study day	Time point
-1	1 (predose)	AM
1	1	PM
	2	AM
2	2	PM
	3	AM
X	X	PM
	X + 1	AM
84	84	PM
	85	AM

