6.2. Primary Estimands and Efficacy Analyses

The estimands selected for the 2 primary endpoints will assess the change from baseline due to the initially randomized treatment as actually taken. These estimands assess the effectiveness at week 12, focusing on the causal effects attributable to the initially randomized medication. The sponsor will make all efforts to avoid study withdrawal in this 12-week study. In instances where a patient decides to discontinue IMP or, more importantly, requires alternative therapy for worsening asthma or an asthma exacerbation, the investigators will be instructed to encourage the patient to continue in the study and return for planned visits until the study completion in order to collect data after IMP discontinuation.

The question of whether to use data collected after IMP discontinuation is an ongoing debate in statistical literature, in particular for studies with symptomatic endpoints and when it is common for patients who dropout to switch therapies ([Mallinckrodt et al 2016](#), [Mallinckrodt 2013](#), [Little and Kang 2015](#), [O'Neill and Temple 2012](#)). This study is designed as a placebo-controlled study and it is expected that patients randomized to placebo would discontinue IMP due to worsening asthma at a higher rate than those randomized to active treatment, which is known to be an efficacious drug as established by multiple studies. After a patient discontinues IMP due to worsening asthma, the patient will be placed on alternative asthma therapies. The first choice will be ICS or a combination of ICS/LABA, exactly the classes of drugs being studied. Other therapeutic choices will include systemic corticosteroids, additional medications other than ICS, or both. All alternatives are proven to alter the spirometry collected after that point and therefore not be appropriate for assessment of IMP effectiveness. Improvement of asthma would be expected as rapidly and early as 1 week for FEV₁ for placebo patients placed on ICS ([Szeffler et al 1999](#)). It has also been shown that patients placed on ICS with long acting beta-agonists can have significant improvement in serial FEV₁ measurements on the same day ([Corren et al 2007](#), [Pearlman et al 1999](#)). Therefore, any patient who discontinued IMP and was placed on alternative therapies would be expected to have rapid and demonstrable improvements in lung function approximating the levels measured at screening.

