6.4. Other Efficacy Endpoints Analysis

The other efficacy endpoints are as follows:

- Change from baseline in weekly average of the total daily (24-hour) use of albuterol/salbutamol inhalation aerosol (number of inhalations) at weeks 4, 8, and 12
- Change from baseline in percentage of rescue-free days (defined as 24-hour periods with no rescue medication usage) during the 12-week treatment period
- Change from baseline in percentage of symptom-free days (defined as 24-hour periods with asthma symptom score of 0) during the 12-week treatment period
- Change from baseline in percentage of asthma-control days (defined as 24-hour periods with asthma symptom score of 0 and no rescue medication usage) during the 12-week treatment period
- Change from baseline in 1-hour postdose percent predicted morning FEV₁ at week 1
- Change from baseline in weekly average of the daily evening PEF over the 12-week treatment period
- Change from baseline in weekly average of the percent predicted trough morning FEV₁ at weeks 1, 2, 4 and 8
- Proportion of patients who achieve at least a 15% increase in morning FEV₁ at 1-hour postdose at day 1 (the RV/TV1), week 1, and week 12

- Change from baseline in asthma control (measured by C-ACT) score at weeks 4, 8, and 12
- Time to consistent onset of effect defined as the decrease from baseline in daily rescue medication use on 3 consecutive days

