6.4.2. Analysis Methods for Other Efficacy Variables

The analysis of the other efficacy variables will be performed on the ITT analysis set without retrieved dropout data.

6.4.2.1. Change from Baseline in the Weekly Average of the Total Daily (24-hour) use of Albuterol/Salbutamol Inhalation Aerosol (Number of Inhalations) at Weeks 4, 8, and 12

The change from baseline in weekly average of total daily (24-hour) use of albuterol/salbutamol inhalation aerosol (number of inhalations) at weeks 4, 8, and 12 will be analyzed using an MMRM with effects due to baseline value, sex, age, (pooled) investigational center, previous therapy (ICS or NCS), week, treatment, and week-by-treatment interaction. No explicit structure will be assumed for the covariance among the repeated measures. However, if there is a convergence problem with unstructured covariance, then a compound symmetry covariance structure will be assumed.

6.4.2.2. Change from Baseline in the Percentage of Rescue-free Days (Defined as 24-hour Periods with no Rescue Medication Usage) During the 12-week Treatment Period

The change from baseline in the percentage of rescue-free days (defined as 24-hour periods with no use of rescue medication recorded in the morning and evening) as recorded in the patient diaries during the 12-week treatment period will be summarized and compared between treatment groups using the Wilcoxon-Mann-Whitney test.

Example SAS code for this analysis:

```
proc npar1way data=salf wilcoxon;
  where treat in ("A", "D");
  class treat;
  var change;
  output out=yyy wilcoxon; run;
```

where: change is the change from baseline in percentage of rescue-free days. The code is executed for each pair of treatment comparisons of interest.

6.4.2.3. Change from Baseline in the Percentage of Symptom-free Days (Defined as 24-hour Periods with Asthma Symptom Score of 0) During the 12-week Treatment Period

The change from baseline in the percentage of symptom-free days (defined as 24-hour periods with asthma symptom scores of zero) as recorded in the patient diaries during the 12-week treatment period will be summarized and will be compared between treatment groups using the Wilcoxon-Mann-Whitney test.

6.4.2.4. Change from Baseline in the Percentage of Asthma-control Days (Defined as 24-hour Periods with Asthma Symptom Score of 0 and no Rescue Medication usage) During the 12-week Treatment Period

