The proportion of patients who achieve at least a 15% increase in morning FEV₁ at 1-hour postdose at day 1 will be analyzed using a logistic regression model with effects due to previous therapy (ICS or NCS) and treatment. The proportion of patients who achieve at least a 12% increase in FEV₁ at 1-hour postdose at week 12 will be analyzed similarly.

6.4.2.9. Change from Baseline in Asthma Control (measure by C-ACT) score at Weeks 4, 8, and 12

The change from baseline in C-ACT score at weeks 4, 8 and 12 will be summarized descriptively by visit and treatment.

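### The week-12 FEV₁ responder analysis uses observed on-IMP data only, so most children who stop IMP leave an ITT-labelled denominator and each arm's response rate is inflated; the effect on the contrast with placebo depends on how dropout splits by arm

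*SAP*

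**What the plan says.** SAP 4.3.1 reserves multiple imputation for the primary endpoints and applies none to MMRM endpoints. For the rest: "For all other variables, only the observed data from the patients will be used in the statistical analyses". SAP 6.4.2 adds: "The analysis of the other efficacy variables will be performed on the ITT analysis set without retrieved dropout data". SAP 3.1 defines the ITT set as all randomized patients.

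The responder endpoint is defined in SAP 1.2 and 6.4, and in Protocol 9.5.3, as a rise of at least 15% in 1-hour postdose morning FEV₁ at day 1, week 1 and week 12. For day 1, SAP 6.4.2.8 says the proportion "will be analyzed using a logistic regression model with effects due to previous therapy (ICS or NCS) and treatment". For week 12 it refers to "at least a 12% increase in FEV₁ at 1-hour postdose at week 12 will be analyzed similarly", so the threshold differs from the definition. It gives no week-1 analysis, and no rule for a child without a week-12 value. Protocol 9.5.4.4 leaves these methods to the SAP.

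Two other passages matter. SAP 4.3.2 says that assessments from an "unscheduled early termination visit will be assigned to the next scheduled visit". SAP 6.2 states that "it is expected that patients randomized to placebo would discontinue IMP due to worsening asthma at a higher rate" than patients on active treatment.

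**The concern.** A logistic model drops any record with no outcome. With post-IMP data removed and nothing filled in, a child who stops IMP generally has no week-12 outcome. The result is a response rate mainly among children still on treatment at week 12, which conditions on something that happens after randomization, under an ITT label.

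This sits badly with the SAP's own reasoning. It expects placebo children to stop because their asthma worsens, and its LOCF/BOCF sensitivity analysis (6.2.2.3) treats stoppers with a positive change as failures. Where the SAP wants something other than observed data for an 'other' endpoint, it says so: 6.4.2.5 substitutes the day-1 postdose value for a missing week-1 value. Section 6.4.2.8 has no such sentence. The only explicit non-responder statement, in Protocol 9.5.4.3, belongs to the endpoint of IMP discontinuation for exacerbation.

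At stake is whether the reported response rates, and possibly the comparison with placebo, describe the randomized groups.

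**Working it through.** **1. The plan's dropout figure.** Protocol 9.1 and SAP 2.4 give 181 evaluable patients per arm and 12% dropout: 181/(1 − 0.12) = 205.7, rounded up to 206, and 4 × 206 = 824. This reproduces. It implies 206 − 181 = 25 children per arm who do not complete treatment. I take 12% as a stand-in for the share who stop IMP (assumption); it is an overall planning figure with no split by arm.

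**2. How many leave the week-12 denominator.** If nothing is carried forward, 12%. If the IMP discontinuation visit (IMPDV) counts as the early termination visit in SAP 4.3.2, a child who stops between week 8 and week 12 supplies a value labelled week 12. With stopping uniform over 12 weeks (assumption), (12 − 8)/12 = 1/3 of stoppers are kept, and 12% × 2/3 = 8% leave. If one sixth to one half are kept, 10% to 6% leave.

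**3. Inflation of each arm's rate.** Let p be the response rate among observed children and d the proportion who stop. Scoring stoppers as non-responders gives p(1 − d), so the observed rate is too high by a factor 1/(1 − d). At d = 12% this is 1/0.88 = 1.136, or 13.6% relative. If late stoppers (4%) are kept, the factor is between 1/0.92 = 1.087 (none of them responds) and 1.136 (they respond as completers do).

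**4. The odds ratio, active v placebo.** The documents give no response rates, so I assume 40% active and 30% placebo among observed children. Observed OR = (0.40/0.60)/(0.30/0.70) = 1.56. With stoppers as non-responders:

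| Dropout, active / placebo | Source | Rates, active v placebo | OR |
|---|---|---|---|
| 12% / 12% | plan's overall figure in both arms | 0.40 × 0.88 = 35.2% v 0.30 × 0.88 = 26.4% | 1.51 |
| 3.1% / 11.2% | sponsor's earlier 6-week study, SAP 6.2 | 0.40 × 0.969 = 38.8% v 0.30 × 0.888 = 26.6% | 1.74 |
| 9.3% / 20% | assumed; (3 × 9.3 + 20)/4 = 12.0 | 0.40 × 0.907 = 36.3% v 0.30 × 0.80 = 24.0% | 1.80 |

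Other assumed response pairs go the same way. For 50% v 35%, the observed OR of 1.86 becomes 1.77 at equal 12% and 2.08 at 3.1%/11.2%. For 30% v 20%, 1.71 becomes 1.68 and 1.90.

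**5. Where the direction changes.** Non-responder scoring widens the risk difference only if p_placebo × d_placebo > p_active × d_active, that is, d_placebo/d_active > p_active/p_placebo. At 40% v 30% the ratio must exceed 1.33; with 12% on active, placebo dropout must exceed 16%. For the OR the break-even is lower. It rises when d_placebo/(1 − p_placebo + p_placebo·d_placebo) exceeds the same expression for active. With 12% on active, the active side is 0.12/(0.60 + 0.048) = 0.185, which placebo reaches at d = 0.137. So on the OR scale placebo dropout must exceed about 13.7% before the observed-data analysis pulls the OR toward 1. The earlier study's ratio is 11.2/3.1 = 3.6.

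**The case against.** A reader might infer that the observed-data rule drops the full 12% and weakens the contrast with placebo. The documents do not support either as a flat statement.

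- **The 12%.** Protocol Table 3 schedules the 1-hour FEV₁ at the IMPDV, and Protocol 3.1 wants that visit before a therapy change where possible. SAP 4.1 defines retrieved dropout data as collected on alternative therapy after IMP stops, so an IMPDV value is not clearly excluded, and SAP 4.3.2 may carry it to week 12. Whether the IMPDV is the visit meant there is not stated. This stands: 12% is an upper figure. The same mapping could also let a child who stopped for worsening asthma count as a week-12 responder.
- **The weakened contrast.** It needs sufficiently higher dropout on placebo. The SAP expects that direction but gives no split for this trial. The 11.2% and 3.1% come from a 6-week study of a different drug in patients aged 12 and over. At a flat 12% the observed-data contrast is slightly overstated. This stands.
- **FS versus Fp.** The documents tie the 1-hour measure to this comparison, and the expected imbalance is placebo against active. Equal dropout is the nearest scenario there, and the OR hardly moves. This stands.
- **Consequence.** The endpoint is outside multiplicity control and was not sized. The same week-12 measurement is a primary endpoint with reference-based imputation for stoppers, and discontinuation for exacerbation is a secondary endpoint. This stands and limits severity.
- **Preference.** Observed data is a prespecified choice, and non-responder scoring labels unrelated withdrawals as failures. True, but the stated choice makes the denominator depend on a post-randomization outcome, and the alternative is standard for a responder endpoint.

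**Conclusion.** The concern holds in a limited form. Sections 4.3.1, 6.4.2 and 6.4.2.8 together remove most children who stop IMP from an ITT-labelled week-12 responder analysis: up to about 12%, or about 8% if IMPDV values map forward and stopping is uniform. If no stopper's value is carried forward, each arm's rate is inflated by 1/(1−d) relative to non-responder scoring, whatever the split.

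The effect on the active-placebo OR is conditional. Under the assumed 40% v 30% response, the observed 1.56 compares with 1.74 at the earlier study's dropout rates and with 1.51 at equal 12%. The first direction is the one the SAP leads one to expect, but the trial's own documents do not establish it.

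Primary and secondary conclusions are unaffected. Severity is low: a cheap improvement.

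**What to change.** In SAP 6.4.2.8, before database lock:

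- State that patients who discontinue IMP or the study before the visit are counted as non-responders, with all randomized patients in the arm as the denominator. With that denominator, a completer without a valid value also needs a stated score.
- State that IMPDV values are not carried to week 12 for this endpoint.
- Keep the observed-case proportion as a supporting summary.
- Reconcile the 12% threshold in the week-12 text with the 15% endpoint definition, and add the missing week-1 analysis.

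The cost is a few sentences and one derivation flag. The downside is that reported rates will be lower and withdrawals unrelated to asthma will be scored as failures; the observed-case summary lets the reader see how much that matters.
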